14.5 Recording of an Adverse Event

Adverse events will be recorded for the duration of a subject's study treatment (following the first dose of Investigational Product, Vigil and/or atezolizumab), and for up to 30 days following the last study treatment or until another therapy has been initiated, whichever is earlier, regardless of causality.

SAEs and AESIs should be recorded for the duration of the study treatment and for up to 30 days following the last study treatment or the initiation of new therapy, whichever is earlier.

All AEs, regardless of causal relationship are to be recorded in the eCRF and source documentation. Additional information about each event, such as treatment required, eventual outcome, and whether or not therapy had to be interrupted or dosages reduced, will be noted in source documents and recorded on the eCRF.

Pre-existing conditions will be recorded at baseline on the Medical History Form. If a preexisting condition does not change, it does not have to be reported as an AE on subsequent cycles.

14.6 Serious Adverse Event Reporting

All SAEs and AESIs will be reported within 24 hours of notification by the site via email or fax to Gradalis, Inc. This includes any death from any cause while a subject is receiving the study agent on this protocol, or \leq 30 days following the last dose of the protocol study agent.

The site will supply as much information as is available at the time of the initial SAE or AESI reporting (study number, subject study number, onset date, relationship, subject demographics, event, dosing regimen of study agent). All SAEs or AESIs must be followed until resolution.

Gradalis, Inc.				
[name] [contact]				
Direct: [contact]	[contact]			

Gradalis, Inc. and Genentech, Inc. will report adverse events to the FDA in compliance with 21 CFR 312.32.

14.7 Overdose

An overdose is defined as a subject receiving a dose of atezolizumab in excess of that specified in the Investigator's Brochure, unless otherwise specified in this protocol.

Any overdose of a study subject with atezolizumab, with or without associated AEs/SAEs, is required to be reported within 24 hours of knowledge of the event to the sponsor and Sponsor Partner Patient Safety or designee using the designated Safety e-mailbox. If the overdose results in an AE, the AE must also be recorded as an AE. Overdose does not automatically make an AE serious, but if the consequences of the overdose are serious, for example death or hospitalization, the event is serious and must be recorded and reported as an SAE. There is currently no specific treatment in the event of an overdose of atezolizumab.

The investigator will use clinical judgment to treat any overdose.

15.0 SUBJECT COMPLETION AND WITHDRAWAL

15.1 Indication for Taking Subjects Off Study

The Investigator must notify the sponsor at any time following discontinuation of a subject on study for the occurrence of a serious or unexpected AE associated with the use of the study medication.

16.0 STATISTICAL CONSIDERATIONS

16.1 Safety Analysis

The safety evaluation will include AEs, AESIs, SAEs, and changes from baseline in laboratory evaluations, vital signs, electrocardiograms, and physical examinations. The number and percentage of subjects reporting treatment emergent AEs will be summarized overall and by the highest Common Terminology Criteria for Adverse Events (CTCAE) grade, system organ class, and preferred term, with a breakdown by dose and tumor type. Similarly, the number and percentage of subjects reporting treatment-emergent AEs considered related to investigational product will be summarized. At each level of subject summarization, a subject will be counted once using the highest grade and level of causality if one or more occurrences of the same system organ class/preferred term is reported. Adverse events will be graded according to the National Cancer Institute (NCI) CTCAE v4.03 and coded using the Medical Dictionary for Regulatory Activities. Laboratory abnormalities will be graded according to the NCI CTCAE v4.03, if applicable.

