3.0 OBJECTIVES

3.1 Primary objective(s)

To evaluate and characterize the tolerability and safety profile of Vigil combined with atezolizumab.

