The primary objective of the study is to determine the safety of the Vigil and atezolizumab combination. Secondary objectives include determination of immune response rate to Vigil alone, atezolizumab alone and the combination of the two agents. In patients with measureable disease, anti-tumor activity as assessed by RECIST 1.1 criteria, will also be summarized and correlated to baseline tumor mutation burden, baseline PD-L1 expression, post treatment TIL infiltration, change in PD-L1 expression and circulating tumor cell response. Overall assessment of time to progression and survival will also be summarized for each cohort. Assuming no untoward adverse effects from the combination of Vigil with atezolizumab, the treatment of 20-25 patients should be sufficient to assess safety and provide an estimate of the immune response rate and RECIST response rate.

 Part 1

The first part will be a safety run-in where the initial 3 subjects registered will receive the combination of Vigil plus atezolizumab. Part 1 will evaluate the safety of Vigil in combination with atezolizumab.

Vigil immunotherapy will be administered at a concentration of 1x10⁷ cells/dose given via intradermal injection every 3 weeks for a minimum of 4 doses and a maximum of 12 doses. Atezolizumab will be administered at the FDA approved dose and schedule as described in the U.S. Package Insert (USPI). Thus, atezolizumab is to be administered at a dose of 1200 mg as an intravenous infusion every 3 weeks. The initial dose is to be administered over one hour and if well tolerated, subsequent infusions may be administered over 30 minutes. Vigil should be administered first, followed 30 minutes later by atezolizumab.

The first subject to receive the combination of Vigil plus atezolizumab must complete the first 21-day cycle of combination therapy without serious, unexpected toxicity before the enrollment of any patients into Part 2 can occur.

Part 2

Part 2 is a randomized, open label intra-patient crossover study of Vigil, the checkpoint inhibitor atezolizumab and the combination of the two agents. Eligible patients will be randomized to receive two cycles of Vigil alone or two cycles of atezolizumab alone, followed by combination treatment with both agents.

Vigil immunotherapy will be administered at a concentration of 1×10^6 or 1×10^7 cells/dose given via intradermal injection every 3 weeks for a minimum of 4 doses and a maximum of 12 doses.

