5.5 Study Enrollment Exclusion Criteria

In addition to the procurement exclusion, subjects (both with Vigil manufactured and undergoing procurement) will NOT be eligible for study registration and enrollment if meeting any of the following criteria:

- 1. Participation in another clinical study with an investigational product within the last 3 weeks prior to study start.
- 2. Receipt of steroid therapy within the 2 weeks of the first dose of study therapy.
- Live vaccine used for the prevention of infectious disease administered < 30 days prior to the start of study therapy. NOTE: Subjects, if enrolled, should not receive live vaccine during the study and for 5 months after the last dose of atezolizumab.
- 4. Post-surgery complication that in the opinion of the treating investigator would interfere with the subject's study participation or make it not in the best interest of the subject to participate.
- 5. Mean QT interval corrected for heart rate (QTc) ≥470 ms calculated from 3 electrocardiograms (ECGs) using Fridericia's Correction.
- 6. Female subjects who are pregnant, breast-feeding or of reproductive potential who are not employing an effective method of birth control defined in the protocol. Effective contraception is required for women receiving atezolizumab for 5 months after the last dose.

- 7. Any condition that, in the opinion of the investigator, would interfere with evaluation of study treatment or interpretation of patient safety or study results.
- 8. Receipt of the last dose of anti-cancer therapy (chemotherapy, immunotherapy, endocrine therapy, targeted therapy, biologic therapy, tumor embolization, monoclonal antibodies, other investigational agent) less than 21 days prior to the first dose of study drug or less than 6 weeks for nitrosourea or mitomycin C.
- 9. Receipt of any anti-cancer therapy between tissue procurement on CL-PTL-126 and first dose of study drug.

Patients should continue the combination of Vigil with atezolizumab until disease progression is documented, or toxicity supervenes. Depending on the number of doses of Vigil manufactured, it is expected that 4 to12 doses of Vigil will be administered. Once Vigil doses are exhausted, subjects whose disease is stable or responding, may continue to receive single agent atezolizumab until disease progression.

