5.6 Withdrawal from Study Treatment

Subjects will be taken off study treatment if any of the following occur:

- 1. An AE that, in the opinion of the Investigator or the Sponsor, contraindicates further dosing.
- 2. Patients with disease progression assessed by RECIST 1.1 criteria as determined by the investigator will not receive further Vigil or atezolizumab treatment.
- 3. The patient experiences unacceptable (≥Grade 3) toxicity felt to be related to treatment with Vigil, atezolizumab, or study related procedure that persists for >2 weeks.
- 4. Persisting Grade 3 or 4 toxicity unrelated to treatment, defined as failing to normalize within 4 weeks.
- 5. \geq Grade 3 allergic reactions related to Vigil or atezolizumab.
- 6. Grade 2 autoimmune reactions unless there is evidence of clinical benefit.
- 7. ≥ Grade 3 autoimmune reactions.
- 8. An intercurrent illness, which would in the judgment of the investigator, affects assessments of clinical status to a significant degree or requires discontinuation of study treatment.
- 9. Non-protocol therapy is administered during study treatment.
- 10. Non-compliant with protocol or treatment.
- 11. Patient refuses to continue treatment.
- 12. Sponsor discontinuation of the protocol.

The date of and reason for discontinuation must be noted in the subject's source document. Every effort should be made to complete the appropriate assessments.

At any time, subjects are free to discontinue Vigil and/or atezolizumab without prejudice to further treatment. A subject who decides to discontinue Vigil and/or atezolizumab will always be asked about the reason(s) for discontinuation and the presence of any AE. If possible, they will be seen and assessed by an Investigator. Adverse events will be recorded from time of first dose of Vigil and/or atezolizumab, throughout the treatment period and including the follow-up period:

- 30 days following the last study treatment or until another therapy has been initiated, whichever is earlier, regardless of causality.
- SAEs and AESIs are to be followed for 30 days after the last dose of study drug or the initiation of new therapy, whichever is earlier.

The Study Physician should be notified of any ongoing AE that may delay treatment or necessitate permanent discontinuation of treatment.

The date of and reason for discontinuation must be noted in the electronic Case Report Form (CRF). Every effort should be made to complete the appropriate assessments.

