6.2.2 Dose Reduction / Escalation

Dose reduction or dose increase is not allowed for Vigil or atezolizumab.

Dose Holding Criteria

Both atezolizumab and Vigil should be held for any of the following AEs. Cycles held for toxicity should be made up (that cycle number is delayed rather than skipped). Atezolizumab and Vigil held may be resumed in patients whose AEs recover to Grade 0-1, with the exception of rash, which should recover to Grade 2 or better.

- Grade 2 pneumonitis
- Aspartate aminotransferase (AST) or alanine aminotransferase (ALT) greater than 3 and up to 5 times upper limit of normal (ULN) or total bilirubin greater than 1.5 and up to 3 times ULN
- Grade 2 or 3 diarrhea or colitis
- Symptomatic hypophysitis, adrenal insufficiency, hypothyroidism, hyperthyroidism, or Grade 3 or 4 hyperglycemia
- Grade 2 ocular inflammatory toxicity
- Grade 2 or 3 pancreatitis, or Grade 3 or 4 increases in amylase or lipase levels (greater than 2.0 times ULN)
- Grade 3 or 4 infection
- Grade 2 infusion-related reactions
- Grade 3 rash
- Grade 2 nephritis

Based on the mechanism of action of atezolizumab leading to T-cell activation and proliferation, there is the possibility of observing immune related Adverse Events (irAEs) during the conduct of this study. Potential irAEs include immune related colitis, pneumonitis, hepatitis, and endocrinopathies. Subjects should be monitored for signs and symptoms of irAEs. Subjects should be monitored for signs and symptoms of irAEs. In the absence of an alternate etiology (e.g., infection or PD) signs or symptoms of colitis, pneumonitis, hepatitis, and endocrinopathy should be considered to be immune-related.

Study Regimen Delay

- Cycles held for toxicity should be made up and not deleted.
- Dosing of atezolizumab and Vigil may be restarted when toxicity is ≤ Grade 1 severity with the exception of rash which may be ≤ Grade 2.
- In case of immune related adverse events, treatment with atezolizumab and Vigil may be delayed for up to 15 weeks (12 weeks for steroid therapy plus 3 weeks for gradual steroid tapering to a dose of ≤ 10 mg/day of prednisone.
- Subjects who delay treatment for more than 15 weeks due to toxicities will be considered off study treatment (see Section 6.3 Withdrawal).

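### The safety tables in Section 16.1 are not split by regimen, so they do not isolate the Vigil plus atezolizumab combination that is the primary objective

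*Combined protocol and SAP*

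**What the plan says.** Section 3.1 gives one primary objective: "To evaluate and characterize the tolerability and safety profile of Vigil combined with atezolizumab".

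Section 16.1 is the analysis meant to serve it. Treatment-emergent adverse events are tabulated overall and by highest CTCAE grade, "system organ class, and preferred term, with a breakdown by dose and tumor type". A further summary covers events related to investigational product, without naming which agent. The counting rule reads: "At each level of subject summarization, a subject will be counted once using the highest grade and level of causality". The synopsis and Section 4.0 describe the same summaries, without the dose and tumor-type breakdown. None of these places splits the tables by study part, Part 2 sequence, regimen or treatment period, or defines a population of combination-treated subjects.

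Several regimens feed these tables:

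- Part 1 gives both agents from the first dose to 3 subjects (Section 4.0).
- Part 2 subjects are "randomized to receive two cycles of Vigil alone or two cycles of atezolizumab alone, followed by combination treatment" (Section 4.0).
- Section 5.5, closing paragraph: "Once Vigil doses are exhausted, subjects whose disease is stable or responding, may continue to receive single agent atezolizumab until disease progression". Section 6.2.2 also provides for atezolizumab alone after a Grade 3 or 4 toxicity attributed to Vigil, and Part 3 is atezolizumab alone after Cycle 12.
- Section 5.6: "At any time, subjects are free to discontinue Vigil and/or atezolizumab without prejudice to further treatment".

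Recording spans all of them: "Adverse events will be recorded from time of first dose of Vigil and/or atezolizumab, throughout the treatment period and including the follow-up period" (Section 5.6, and to the same effect Section 14.5).

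**The concern.** A table that follows Section 16.1 exactly puts events from the single-agent lead-in, the combination and atezolizumab after Vigil into the same cells. A reader could not tell which events began on the combination, or how many combination-exposed subjects a percentage refers to. Part 2 subjects who stop during the lead-in stay in the overall denominator although they never received both agents.

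The counting rule hides the regimen further. Suppose a subject has a Grade 3 event in the lead-in and a Grade 2 event of the same preferred term on the combination. She becomes one Grade 3 entry with no regimen attached.

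The plan does distinguish regimens elsewhere. Section 3.2 asks for immune response to each agent and to the combination, and Section 16.2 analyses response, PFS and OS by cohort. The primary objective has no comparable separation. Section 16.3 says the results will help design later studies, so the combination's own profile is what those designers will look for.

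**Working it through.** Section 16.1 gives no figure to reproduce, so the check is whether its breakdowns separate regimens, and how much of the schedule is combination treatment.

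**Does dose separate regimens?** Atezolizumab has one dose, 1200 mg. Only the Vigil cell dose varies (1×10^6 or 1×10^7 in Part 2; 1×10^7 in Part 1), and Section 6.2.2 states: "Dose reduction or dose increase is not allowed for Vigil or atezolizumab". Section 16.1 does not define dose, but the two Vigil cell doses are the natural reading. In Part 2 either one can be given alone and then with atezolizumab, so each dose column still mixes regimens. In the atezolizumab-first sequence, lead-in events occur before any Vigil is given. Grade, system organ class, preferred term, relatedness and tumor type do not identify the regimen either.

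**How many subjects start on a single agent?** Inputs: N = 20 to 25 (Section 5.1) and 3 subjects in Part 1 (Section 4.0). Part 3 continues Part 2 subjects, so the remainder enter through Part 2.

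- N = 20: 20 − 3 = 17; 17/20 = 85%.
- N = 25: 25 − 3 = 22; 22/25 = 88%.

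**How much of a full course is combination treatment?** Inputs: 4 to 12 Vigil doses, two single-agent cycles, Cycles 1 to 12 (Section 4.0, Appendix B), with atezolizumab continuing after the last vial. Let v be the number of vials. Combination cycles are v − 2 for Vigil first, and the smaller of v and 10 for atezolizumab first.

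| Vials | Sequence | Combination cycles | Share of 12 |
|---|---|---|---|
| 4 | Vigil first | 4 − 2 = 2 | 17% |
| 4 | Atezolizumab first | 4 | 33% |
| 12 | Vigil first | 12 − 2 = 10 | 83% |
| 12 | Atezolizumab first | 10 | 83% |

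Even in Part 1, a subject with 4 vials who completes 12 cycles has 4 combination cycles and then 8 of atezolizumab alone. Part 3 adds more atezolizumab-alone cycles.

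**How many subjects in the denominator ever receive both agents?** The documents give no stopping rate. As an assumption, let 0% to 30% of Part 2 subjects stop before Cycle 3. At 30%, (3 + 0.7 × 17)/20 = 14.9/20 = 74.5% and (3 + 0.7 × 22)/25 = 18.4/25 = 73.6%; at 0% the share is 100%.

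**Would raw percentages by regimen be enough?** No, because the periods differ in length. As an illustration only, assume the same 3% risk per cycle on every regimen, with independent cycles. A two-cycle lead-in then shows 1 − 0.97^2 = 5.9% of subjects with an event, and ten combination cycles show 1 − 0.97^10 = 26.3%. That is 4.5 times as many with no true difference, so a regimen table has to report exposure.

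**The case against.** An overall table from first dose is a legitimate summary of the whole planned sequence, and Part 1 evaluates the combination from the first dose. The study is descriptive, its sample size has no statistical basis (Section 16.3), and no decision rule uses this table. Administration of both drugs is recorded in the CRF (Section 9.1) and toxicity is assessed every cycle (Appendix B), so a combination table could be derived later.

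Most of this stands. The overall table is not wrong and should stay; what is missing is an additional table. Part 1 is not a substitute: it has 3 subjects, and Section 16.1 does not tabulate it separately. Later derivation is possible, but the denominator, the period boundaries and the carry-over rule would then be chosen with open-label data from 20 to 25 subjects in view.

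A reader might infer something stronger: that the pooled percentages overstate, or understate, the combination's percentages by some calculable factor. The documents do not support that. Any factor needs event risks per regimen, stopping rates and a vial distribution, and none is given. It would also largely reflect the length of follow-up, since percentages over 12 cycles and over 2 to 4 cycles differ even when the risk per cycle is identical.

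**Conclusion.** The point holds as a gap in the specified analysis: the tables in Section 16.1 do not answer the primary objective, because nothing in them isolates the combination. What the documents establish is its reach. 85% to 88% of subjects start with two single-agent cycles, and 17% to 83% of the cycles in a full Part 2 course are combination cycles. These figures assume that everyone outside Part 1 enters through Part 2 and, for the cycle shares, that 12 cycles are completed. Neither the direction nor the size of any distortion in event percentages can be stated.

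This should be fixed before analysis. It does not invalidate the trial or lose data.

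**What to change.** Keep the overall table and add a paragraph to Section 16.1 along these lines:

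> Treatment-emergent adverse events will also be tabulated by regimen at onset: Vigil alone (lead-in), atezolizumab alone (lead-in), combination, and atezolizumab alone after Vigil, including Part 3. Within each period a subject is counted once per system organ class and preferred term, at the highest grade in that period. The denominator for the combination is all subjects who received both agents in at least one cycle. Each column will report the number of subjects, cycles or person-time of exposure, and exposure-adjusted rates. Events near a change of regimen are assigned by a pre-stated carry-over rule, which is a convention. A sensitivity table will count all adverse events from the first combination dose onward.

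Any Vigil-alone cycles after atezolizumab is stopped, which Section 5.6 allows, can be listed separately. The plan must choose and justify its own carry-over window. The 30 days in Section 14.5 run from the last study treatment and do not settle how to treat a subject who continues on atezolizumab.

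The cost is one paragraph and the added tables, with no new data collection. The downsides are small denominators per column, periods of unequal length (hence the exposure-adjusted rates), and attribution near a regimen change that remains a convention.

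A separate item also needs reconciling: the toxicity row in Appendix C names only AESIs and SAEs, while Section 14.5 requires all adverse events to be recorded.

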Of the Vigil treated patients, 4 out of 27 had rapidly progressive disease after 1 or 2 injections of Vigil and were removed from study. The remaining 23 patients had stable disease as their best response to therapy and received between 3 and 11 monthly injections of Vigil. Median survival of the Vigil treated patients was 554 days when measured from tissue procurement and was not reached when measured from start of Vigil treatment. The 18 patients who had tumor harvested but did not receive Vigil therapy survived a median of 132 days from tissue procurement (p < 0.0001). There were no apparent differences in response to treatment, survival or safety profile by dose level of the Vigil construct.

The interferon gamma ELISPOT assay was piloted as a clinical biomarker of immune activation in 18 of 27 Vigil treated patients on the study. Only 1 of 18 patients demonstrated immune activation at baseline. Nine of 18 patients converted to ELISPOT positivity by month 4 of Vigil treatment and remained positive throughout treatment and in some cases for up to 6 months afterwards. A tenth patient was noted to convert to ELISPOT positivity at 6 months after the start of Vigil. Interestingly, the survival of ELISPOT positive patients was significantly longer than that of patients who failed to convert to positivity (p = 0.045 from time of tissue procurement or p = 0.025 from start of Vigil treatment).

The association of TGF β expression with poor outcome in ovarian cancer coupled with the safety, biomarker and survival correlations reported in the first-in-human study, provided the basis for a randomized Phase 2 study of Vigil Immunotherapy as maintenance therapy in women who achieved complete clinical response (cCR) following surgical de-bulking and standard, paclitaxel/carboplatin chemotherapy. Following surgery and chemotherapy, patients in the control arm underwent regular observation for recurrence, which is current standard of care (SOC). Patients randomized to the control arm were permitted to cross-over and receive their Vigil at the time of recurrence.

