Eligible patients were initially randomized 2 (Vigil): 1 (SOC). Patients received 1.0×10^7 cells / intradermal injection of Vigil once per month for up to 12 doses as long as sufficient material was available. Tumor procurement needed to be sufficient to supply a minimum of 4 monthly injections in order for a patient to be entered into the study. Treatment was continued until disease recurrence or exhaustion of the patient's vaccine supply. Clinical adverse events, as reported by the patient, were assessed continuously. Other scheduled safety assessments included monthly physical examination, performance status, height, weight, vital signs and laboratory evaluations. The primary efficacy endpoint was recurrence free survival assessed radiographically by the investigators. CA-125 was monitored at baseline, monthly for the first year, every 3 months \pm 2 weeks for the second and third year.

Serial immune function analysis including ELISPOT analysis of mononuclear cell function to pre-processed autologous tumor cells was monitored at baseline (screening), prior to Vigil injection and at Months 2, 4, 6 and at end of treatment (EOT). A positive response was defined as > 10 ELISPOTs induced per 10⁶ peripheral blood mononuclear cells (PBMC) and twice baseline response.

Results are reported in a total of 42 patients, 31 in the Vigil arm and 11 in the control arm. The original randomized design was abandoned after 21 patients were randomized into the Vigil arm of the study and 11 to the control arm, when the sponsor decided to initiate a definitive Phase 3 study. At that time, an additional 10 patients who were completing chemotherapy were allowed to receive Vigil without randomization.

A total of 241 intradermal (ID) injections of Vigil were administered to the 31 patients. The most frequent treatment emergent adverse events, considered related to therapy were injection site reactions of CTCAE Grade 1 or 2, which occurred in essentially all Vigil treated patients. There were no CTCAE Grade 3 or 4 treatment related adverse events amongst the Vigil treated patients.

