Part 2, radiological assessment of tumor response will be performed at baseline, at the end of cycle 2 of single agent therapy and every third cycle thereafter. Tumor biopsy for correlative studies including scoring of tumor infiltrating lymphocyte (TIL) and PD-1 / PD-L1 expression analysis will be obtained at tissue procurement, prior to the start of combination therapy and at any time after the end of cycle 3. Whole blood for correlative studies (immune function) will be obtained at baseline, at the start of cycle 3 (the first cycle of combination therapy) and every third cycle thereafter.

Part 3 schedule of assessments are noted in Appendix C. The schedule will continue from Part 2 in which the following will be assessed every third cycle: radiological assessments, tumor biopsy (if available), and whole blood collection for correlative studies.

The safety evaluation will include all adverse events (AEs), serious adverse events (SAEs) and adverse events of special interest (AESIs) as well as changes from baseline in laboratory evaluations, vital signs, electrocardiograms, and physical examinations. The number and percentage of subjects reporting treatment emergent AEs will be summarized overall and by the worst Common Terminology Criteria for Adverse Events (CTCAE) grade, system organ class, and preferred term. Similarly, the number and percentage of subjects reporting treatment-emergent AEs considered related to investigational product will be summarized. At each level of subject summarization, a subject will be counted once using the highest grade and level of causality if one or more occurrences of the same system organ class/preferred term is reported. Adverse events will be graded according to the National Cancer Institute (NCI) CTCAE v4.03

and coded using the Medical Dictionary for Regulatory Activities. Laboratory abnormalities will be graded according to the NCI CTCAE v4.03, if applicable.

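### The adverse-event summaries in Section 16.1 are not split by treatment received, so they do not isolate the safety of the combination, which is the primary objective

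*Combined protocol and SAP*

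**What the plan says.** Section 3.1 gives the primary objective: "To evaluate and characterize the tolerability and safety profile of Vigil combined with atezolizumab".

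In Part 1, three subjects receive both agents from Cycle 1. Part 2 subjects are randomised to "two cycles of Vigil alone or two cycles of atezolizumab alone, followed by combination treatment with both agents" (Section 4.0). Part 2 imaging falls "at the end of cycle 2 of single agent therapy and every third cycle thereafter", and under Section 5.6, item 2, subjects who have progressed "will not receive further Vigil or atezolizumab treatment". Section 6.4 allows selected exceptions. The closing paragraph of Section 5.5 lets stable or responding subjects carry on with atezolizumab alone after their Vigil supply ends, and Part 3 continues it after Cycle 12.

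Section 16.1 summarises treatment-emergent events overall and by worst grade, "system organ class, and preferred term, with a breakdown by dose and tumor type". Related events are summarised in the same way, as related to study product without naming the agent. Each subject enters once per term, at the worst grade. Section 4.0 and the Synopsis describe the same summaries with no breakdown. Reporting by cohort is mentioned only for response, progression and survival (Sections 4.0 and 16.2).

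On collection, Section 14.5 requires every adverse event to be recorded from first dose until up to 30 days after the last study treatment, with no Part 3 exception. The Appendix B toxicity row agrees. The Appendix C row, for Part 3, names only AESIs and SAEs.

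**The concern.** If the plan is followed exactly, the overall table mixes events from the single-agent lead-in, from the combination, and from atezolizumab given after Vigil has stopped. It also counts subjects who never received both agents. A Grade 3 autoimmune reaction during an atezolizumab-alone lead-in, for example, ends treatment under Section 5.6, item 7, before any combination dose. It would still appear in the summary offered for the combination objective.

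Section 14.3 treats systemic immune activation as a potential risk when atezolizumab is given with other immunomodulating agents, so toxicity under joint exposure is the question of interest. Section 16.3 says the results will help design later studies, and those designers need to know which events began, or worsened, on both agents.

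The Appendix C row is a smaller, separate problem. Sites cannot tell whether non-serious events outside the AESI list should be collected at Part 3 visits.

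**Working it through.** **1. Can an existing breakdown stand in for treatment period?**

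- *Dose.* Atezolizumab is fixed at 1200 mg. Vigil is given at one of two levels, and Section 6.2.2 bars dose changes. Nothing ties a Vigil level to single-agent or combination cycles, so dose does not identify period.
- *Tumor type.* This is a baseline feature, constant across periods.
- *Relatedness.* Section 14.1 records a relationship for each event, but Section 16.1 reports it without agent or period.
- *Count-once rule.* A lead-in event at the worst grade can represent the subject for that term.

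None of them separates the periods.

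**2. Lead-in share of exposure.** For a Part 2 subject who receives c cycles (c ≥ 2), the lead-in share is 2/c:

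| c | Lead-in share |
|---|---|
| 12 | 2/12 = 17% |
| 6 | 2/6 = 33% |
| 4 | 2/4 = 50% |
| 3 | 2/3 = 67% |
| 2 | 2/2 = 100% (never on the combination) |

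Part 1 subjects have no lead-in.

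**3. Cycles after Vigil runs out.** Let v be the number of vials, at least 4 by Section 5.4. Assume one vial per dose and treatment through Cycle 12.

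- Vigil-first: lead-in 2, combination v − 2, post-combination 12 − v.
- Atezolizumab-first: lead-in 2, combination min(v, 10), post-combination 10 − min(v, 10).
- Part 1: combination v, post-combination 12 − v.

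| v | Vigil-first | Atezolizumab-first | Part 1 |
|---|---|---|---|
| 4 | 2/2/8 | 2/4/6 | 0/4/8 |
| 8 | 2/6/4 | 2/8/2 | 0/8/4 |
| 12 | 2/10/0 | 2/10/0 | 0/12/0 |

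In every Part 2 cell, combination plus post-combination is 10 of 12 cycles. The vial count moves cycles between those two periods and leaves the lead-in unchanged.

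**4. Is the post-combination period clean?** No. In the first-in-human study, subjects who converted on the immune assay "remained positive throughout treatment and in some cases for up to 6 months afterwards" (Section 1.4). It therefore needs its own column, and also a pooled column with the combination.

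**5. Subjects never on the combination.** Part 2 has 20 − 3 = 17 to 25 − 3 = 22 subjects. If a share d stops before Cycle 3, the number exposed to the combination is 3 + (1 − d) × 17 or 3 + (1 − d) × 22. The documents do not give d. Over an assumed range of 0 to 30%, this gives 20 down to 14.9 of 20, or 25 down to 18.4 of 25. As an illustration, with 3 of 20 never exposed, an event in 4 combination subjects reads 4/20 = 20% in the overall table and 4/17 = 24% among those exposed.

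**6. Precision of a split.** With 1:1 allocation (assumed; the ratio is not stated) each lead-in arm has about 8 to 11 subjects. With zero events the two-sided exact 95% upper bound is 1 − 0.025^(1/n): 36.9% at n = 8 and 28.5% at n = 11. The split can only be descriptive.

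**The case against.** The strongest reply is that nothing is lost. Toxicity is assessed every cycle in Parts 1 and 2 (Appendix B) and dosing goes into the CRF (Section 9.1), so a period split could be produced later. Section 16.1 also covers related events, laboratory values, vital signs, ECGs and examinations. The study is descriptive, with a sample size not set on statistical grounds, and period columns will be thin. All of this is correct, and it limits the point to what the plan specifies for analysis. It does not supply the missing split, and leaving the allocation rule until the data are known invites arguable choices.

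Some stronger readings are tempting, and the documents do not support them:

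- *Combination cycles are only 17% to 33% of exposure.* This takes the 4-vial Part 2 rows (2/12 and 4/12), assumes 12 cycles, and treats atezolizumab after Vigil as clean single-agent exposure, which carry-over contradicts. Stopping after Cycle 6 with 4 vials gives 2/6 = 33% and 4/6 = 67%. The vial distribution is not stated. In an earlier ovarian study, "A total of 241 intradermal (ID) injections of Vigil were administered to the 31 patients", which averages 241/31 = 7.8.
- *About three Part 2 subjects will never reach the combination.* This borrows from the first-in-human study, where "4 out of 27 had rapidly progressive disease after 1 or 2 injections of Vigil and were removed from study" (4/27 = 15%, exact 95% CI 4% to 34%). That study included men, gave Vigil monthly and had no atezolizumab lead-in. Section 6.4 also lets some subjects continue past progression.
- *The overall table is biased in a known direction.* Lead-in events add to the numerator and never-exposed subjects add to the denominator; the net effect is not determined. The exact 95% intervals for 4/20 and 4/17 are 6% to 44% and 7% to 50%.
- *Section 6.6 needs rewording too.* Its wording concerns entry to Part 3, not the adverse-event tables, and Section 5.5 already lets stable or responding subjects continue atezolizumab.

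**Conclusion.** The point holds as a gap in the planned analysis. The adverse-event summaries do not isolate combination events or combination-exposed subjects, although that is the primary objective, and no other section fills the gap. What is certain is the two-cycle lead-in for every Part 2 subject: 17% of cycles at 12 cycles, more with earlier stopping. The number who never receive the combination, and the amount of post-Vigil atezolizumab exposure, cannot be estimated from the documents. The cycle counts rest on one vial per dose and treatment through Cycle 12.

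The Appendix C row conflicts with Section 14.5. A reader might infer that non-serious Part 3 events will go uncollected, but the general text requires all events, so the conflict shows only that sites could read it either way. It concerns atezolizumab alone after Cycle 12 and bears little on the combination objective.

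Both changes should be made. Neither gap undermines the trial.

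**What to change.** 1. Keep the overall tables in Section 16.1. Add a descriptive table of treatment-emergent events by treatment period: Vigil-alone lead-in, atezolizumab-alone lead-in, combination, atezolizumab after combination, and the last two pooled.
2. Use subjects who entered each period as its denominator and show cycles at risk. Include Part 1 under combination.
3. Assign an event to the period of the last dose before onset. If it worsens in grade in a later period, count it there as a new treatment-emergent event at the worsened grade. Otherwise a Grade 1 transaminase rise that begins in the lead-in and reaches Grade 4 on the combination would be shown only under the lead-in.
4. Section 4.0 allows subjects who have already had Vigil on this study to re-enter Part 2. Report the second course separately, not as a combination-naive lead-in.
5. Change the Appendix C toxicity row to all adverse events, to match Section 14.5 and Appendix B.

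The cost is extra programming, including the worsening and re-enrolment rules, and one corrected row label. No visits or subjects are added. The columns will be sparse and delayed immune events will be attributed imperfectly, so the table should be labelled descriptive.
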